All contact professionals and PBRN/CREATE sites will be involved prior to study initiation, educated about this study, and engaged in facilitating outreach and care. It is noteworthy that our research team's studies that use focus groups and telephone interviews with more intensive questions about sexual assault in RNG populations have not resulted in any subsequent clinical emergencies. Women who have no positive screens will be able to access the same educational information and web links if they choose to. The web-based post-screening survey immediately following the screening and education interface will be revised from our original web-and semi-structured survey to include satisfaction with information about VA MH and EBP for PTSD that they receive in the web education intervention. We will also repeat the check-list of barriers and facilitators to VA MH care and to PTSD EBP tailored from the participant's prior responses to determine if the web-based intervention altered their perceptions. We will also query those who are PTSD positive and who are not engaged in PTSD EBP and other MH care whether they intend to seek care as a result of their participation and why or why not. Participants will be reimbursed \$30.00 for the time and effort to complete the web-interface and pre-and post-surveys. If they complete the web-interface and pre and post surveys within two weeks following their initial postal or e-mail invitation then they will receive an additional \$10.00. In order to receive subject reimbursement, participants will be asked to provide their names and social security number to the coordinator through a toll-free number. These data and linkage study ID number will be maintained in a locked and limited access research network electronic file behind the VA firewall. With these subject identifiers we are able to access participant VA records, given subject IRB consent. VA health services utilization will be obtained from all consenting participants in this phase of the study, including initiation of mental health services (either in primary care or specialty care) and extent of participation in EBP. Participation will be measured by self-report of EBP engagement, type, and number of sessions. This will be validated by VA electronic chart review.

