local VA mental health and PTSD evaluation and treatment in the Veteran's locale, or 2) OEF/OIF/OND outreach coordinators in place at every VA. A toll-free number will be provided to participants assigned to the NCM with information that they can initiate contact and that they otherwise will be telephoned by the NCM within 2 weeks following completion of the post-intervention survey. Pharos Innovations (web-interface developer) will provide immediate notification to the study NCM of participants who are assigned to each group and she will be able to access web results of participant study screens. Upon telephone contact with the participant, the concierge NCM will engage the patient and by telephone administer a 17 item PTSD Checklist (PCL) developed by the National Center for PTSD to assess the presence of DSM-IV criteria for PTSD. She will use the PCL-S that allows identification of a specific traumatic event. This will assist with PTSD validation and allow for individualized referral. The NCM will then follow shared decision making protocols for specific domains (Joosten et al., 2008). Domains include (pending focus group augmentation): 1) Actively reporting all information and PTSD treatment possibilities to the patient/consumer. The NCM can recommend an option but PTSD treatment and therapy are decided jointly; 2) Encourages the patient to discuss preferences and form their own judgment regarding the harms and benefits of PTSD treatment/EBP options; 3) Makes sure that the information exchange is two-way between patient and NCM; 4) NCM informs partner or key family members who the Veteran includes in the telephone interface in the PTSD treatment decision-making process; 5) Informs Veteran about routes of access to VA or if already enrolled ways to access PTSD EBP and facilitates as needed and actively links with care; and 6) Addresses barriers and facilitators checked by the Veteran on her web-based interface and assists the Veteran in addressing these (e.g., education regarding night clinics, transportation). The NCM will review all PTSD treatment options, including pharmacotherapy and site specific options, e.g. unique groups. Subjects will be educated about the efficacy, risks and benefits, duration of each treatment option. Participants are welcome to re-contact the NCM on our toll free number for further questions and assistance with care initiation or transitions during the duration of the study. However, the NCM will not initiate further follow-up. The study concierge NCM, [name], R.N., M.S. will build on her own skills as a career Army nurse and prior OEF/OIF outreach counselor. She will be trained in the intervention protocol by PI ([name]) and co-I (MV) who are MH care professionals with unique clinical and research expertise specific to this intervention. NCM model fidelity and tools developed (manual, check lists for PTSD and MH utilization, satisfaction) will be guided by consultant [name], who has expertise specifically useful to this with his work with the VA's Translating Initiatives for Depression into Effective Solutions (TIDES) project in his QUERI implementation expert role. It should be noted that the NCM will use VA/DoD Clinical Practice Guidelines for The Management of PTSD (<http://www.healthquality.vagov>) for assistance with patient education, management, and tracking utilization specific to EBP but also other PTSD treatment interventions documented on the treatment checklist tracking utilization in post-intervention follow-up. Use of PBRN and CREATE study sites will allow NCM interface with PC, WHC, and MH teams already sophisticated about and engaged in evolving women's health care and research. This existing infrastructure of relationships and resources will facilitate the successful implementation and evaluation of the NCM linkage intervention. Traditional OEF/OIF/OND outreach counselors educate returning Veterans about their VA eligibility, facilitate enrollment and subsequent appointment scheduling. The NCM will have a complementary role in that her interventions will be specific to PTSD and EBP treatment.

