
**Post-Intervention Follow-up:** Women who screened positive for PTSD and were randomly assigned to NCM or usual OEF/OIF/OND outreach VA PTSD treatment access route will be contacted by the study research coordinator by telephone at 6 and 12 months following web-based interface. The study coordinator will use an IRB approved call contact protocol varying times of day and days of week (used successfully by this team) and ask willing participants brief questions using computer-assisted telephone interview data collection.

Satisfaction with access route and consumer feedback regarding these will be assessed. Those who did not engage in VA MH or EBP will be queried to determine if they have sought non-VA care for their PTSD, including EBP, and current factors influencing needed PTSD services. Using DMDC data, this group will be compared to VA users with regard to access and military characteristics (e.g. rank, number of deployments) in addition to web-based screening data. Women who did engage in VA MH or EBP will be asked about their experiences and satisfaction with EBP and VA care. VA service use will be validated by electronic records. Participants will be also asked about their current satisfaction with the effectiveness of the web-based interface and subsequent utilization of educational links. Non-users will be asked about current barriers to VA and MH services and again offered assistance with access to VA care and EBP if desired. We will use DMDC data to provide comparison to women who initially screened positive for PTSD. Women completing the 6 and 12 month follow-up interviews will be reimbursed \$15.00 for each completed interview.

Sample Size Analysis and Statistical Plan: The pre- and post-satisfaction surveys integrated within the Phase 2 web-based interface will be analyzed to estimate prevalence of post-deployment mental health concerns, pre-interface knowledge and current health care use, and post-interface knowledge, satisfaction, and participants' intentions to seek services for mental health care needs identified through the web-based screening.

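### EBP uptake and non-VA care are collected with no masking to arm, and the nurse's utilization checklist has no defined place among the outcome sources

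*Combined protocol and SAP*

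**What the plan says.** All of this is in section 4.0 of the combined protocol and SAP, under Phase 2.

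- **VA records.** The Phase 2 Intervention Process text says "VA health services utilization will be obtained from all consenting participants in this phase of the study". This covers starting MH services and the extent of EBP participation. The same text makes self-report the measure of EBP engagement, type and session count, with validation by review of the VA electronic chart.
- **Powered outcome.** The statistical plan says MH service use can be measured for all participants from VA databases. It quotes 81% power for a 25-point difference between NCM and outreach.
- **The NCM.** Under Random Assignment to Route of VA PTSD EBP Access, the web developer "will provide immediate notification to the study NCM of participants who are assigned to each group". The NCM uses practice guidelines for education, management and tracking of EBP and other PTSD treatment, "documented on the treatment checklist tracking utilization in post-intervention follow-up". Women assigned to her may call back throughout the study. "However, the NCM will not initiate further follow-up".
- **Follow-up.** Under Post-Intervention Follow-up, women in both arms "will be contacted by the study research coordinator by telephone at 6 and 12 months following web-based interface". The coordinator will "ask willing participants brief questions using computer-assisted telephone interview data collection". In that contact, "Satisfaction with access route and consumer feedback regarding these will be assessed". Women who did not engage in VA MH care or EBP are asked about non-VA care, with no record check described. VA use is validated from electronic records.

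**The concern.** Starting EBP is one of the two outcomes in Hypothesis 2.b. Unlike MH service use, its stated measure is what a woman reports, so it depends on how she is asked and how her answer is coded. If the interviewer learns the arm before those items are recorded, probing and coding can differ by arm without anyone intending it. The statistical plan says the team expects a large effect of the NCM, so an interviewer who shares that view would tend to err in that direction. Non-VA EBP is more exposed, because no record is described against which to check it.

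The checklist is a second, separate gap. The NCM is the intervention under test, knows the assignments and has a stated role in tracking treatment use. No comparable recorder is described for the outreach arm. If her entries were used to classify EBP initiation, one arm would have an extra source of events. The plan neither says that they are used nor rules it out.

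**Working it through.** **Step 1: set the sources side by side, outcome by outcome.**

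| Outcome | Source in the plan | Same source in both arms? | Masking stated? |
|---|---|---|---|
| MH service use (powered) | VA databases, all participants | Yes | Not stated; little room for judgment |
| VA EBP initiation and sessions | Self-report, validated by VA chart | Yes, unless the NCM checklist is also used | No, for interviewer or chart reviewer |
| Non-VA care, including EBP | Interview, only of women without VA MH or EBP engagement | Yes | No |

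No rule says which source decides if self-report, chart and checklist disagree.

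**Step 2: where is the EBP self-report taken?** The text does not name the contact. The five Phase 2 steps put both web surveys before randomization, so those surveys cannot record EBP started afterward. The coordinator's 6- and 12-month calls are the only described post-randomization contact common to both arms. It is therefore a reasonable inference, not a stated fact, that the self-report comes from the interview that also asks about the route.

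**Step 3: who completes the checklist?** The sentence about the NCM places it in post-intervention follow-up. That is the heading under which the coordinator calls both arms, and the NCM initiates no follow-up herself. Three readings fit: an NCM record of intervention contacts and inbound calls, a coordinator's form used for both arms, or both. The text does not settle which.

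**Step 4: reproduce the plan's power figure.** Inputs: at least 120 women screening positive (Sample Size paragraph) and a 25-point difference. Assumed, because not stated: 1:1 allocation (60 per arm), two-sided 5% test, outreach rate 25%.

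Power = Φ[(d − 1.96·SE0)/SE1], where SE0 = √(2·p̄(1−p̄)/n) and SE1 = √([p1(1−p1)+p2(1−p2)]/n).

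- p1 = 0.50, p2 = 0.25, p̄ = 0.375, n = 60
- SE0 = √(2×0.375×0.625/60) = 0.0884
- SE1 = √((0.25+0.1875)/60) = 0.0854
- Power = Φ[(0.25 − 0.1732)/0.0854] = Φ(0.90) = 81.6%

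The stated 81% is reproduced at this rate. Across outreach rates of 5% to 50%, power runs from about 79% to 96%. This outcome is read from databases for everyone, so the present point does not touch it.

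**Step 5: what unequal capture would do to an outcome that depends on report.** The capture rates are hypothetical; the documents give none. Let the true rate p be the same in both arms, with capture s1 (NCM) and s2 (outreach). Recorded rates are p·s1 and p·s2. The false-positive rate is the chance that the same test rejects in either direction.

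Example: p = 0.30, s1 = 1, s2 = 0.8. Recorded rates are 30% and 24%, SE0 = 0.0811 and SE1 = 0.0809. Rejection = Φ[(0.06−0.1589)/0.0809] + Φ[(−0.06−0.1589)/0.0809] = 0.111 + 0.003 = 11.4%.

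| Capture, NCM v outreach | p = 20% | p = 30% | p = 40% | p = 50% |
|---|---|---|---|---|
| 100% v 100% | 5.0% | 5.0% | 5.0% | 5.0% |
| 100% v 90% | 5.9% | 6.5% | 7.3% | 8.5% |
| 100% v 80% | 8.8% | 11.4% | 14.9% | 19.5% |

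With equal capture the rate stays at 5%. That is why the database outcome is safe, and why letting records decide VA EBP would largely protect that outcome too.

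**The case against.** The strongest reply is that the plan already has the main safeguards. One coordinator interviews both arms, VA utilization is obtained for every consenting participant, EBP self-report is validated by chart, and the powered comparison uses VA databases. All of this stands, and it confines the point to EBP and non-VA care.

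Four stronger readings are tempting, and the documents do not support them.

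- *A reader might infer that service use in general is ascertained unequally.* For VA MH use this is wrong, for the reasons just given.
- *A reader might infer that the NCM records outcomes for her own arm.* No text limits the checklist to her arm or makes it an outcome source. It may be a fidelity record, since utilization checklists are also listed among the tools developed alongside model fidelity. A bar on outbound calls also does not prevent her noting treatment on inbound ones, so the two statements about her role are unclear together rather than flatly contradictory.
- *A reader might infer that the interviewer asks about the route first.* The paragraph mentions it first, but that is narrative; the interview script is not in the documents.
- *A reader might put a size on the checklist.* Suppose 30% truly start EBP in both arms, the calls capture 60% or 90% of them, and the checklist recovers half of those missed. Recorded use is then 0.30×(0.6+0.2) = 24.0% v 18.0%, or 0.30×(0.9+0.05) = 28.5% v 27.0%, a false gap of 6 or 1.5 points. This requires the checklist to feed the EBP outcome and no VA record to recover a missed case. The first is stated nowhere, and the second ignores the utilization data and chart validation. It is hypothetical only.

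What the reply leaves open is that validation is not adjudication. No source is named as decisive, the chart reviewer is not masked, and non-VA care has no record behind it.

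**Conclusion.** The point holds for EBP initiation and extent and for non-VA care, and not for MH service use. Arm-aware ascertainment is possible because the route question is likely to disclose the arm and no masking is described. The checklist's owner, coverage and use are undefined. The documents do not show that bias would occur, and its size cannot be derived from them. The rejection rates above rest on assumed capture rates, 60 women per arm, 1:1 allocation and a two-sided 5% test. They show only that a modest difference in capture would matter at this sample size. Because the remedy costs almost nothing and protects a stated hypothesis, the change should be made. It is not a reason to doubt the powered comparison.

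**What to change.** 1. State that any checklist completed by the NCM is a process and fidelity record and is not a source for MH-use or EBP outcomes. Reconcile the Random Assignment text with the Post-Intervention Follow-up text, so that it is clear who completes which form and for which women. Her intervention duties need not change.
2. State that VA records decide VA EBP initiation and number of sessions in both arms, abstracted by existing staff unaware of arm, with self-report as supporting data.
3. Program the computer-assisted interview so that arm is not displayed, and so that all service-use, EBP and non-VA care items are entered and locked before the access-route items appear.

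The cost is protocol wording and a minor re-ordering of the script, with no extra calls, staff or data sources. Two limits remain: a woman may still disclose her arm unprompted, and non-VA care will still rest on self-report, so results on it should be labeled that way.

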Findings from our recently completed Mental Health QUERI RRP (N=131) indicated that **RNG servicewomen completing online screening have substantial post-deployment mental health and readjustment concerns.** Nine post-deployment online screens (for PTSD, depression, substance abuse, prescription drug abuse, military sexual trauma (MST), traumatic brain injury (TBI), family readjustment, combat exposures) were implemented. Less than 1% (n=1) of participants screened negatively for all mental health issues and deployment trauma exposures (recognizing the probable selection bias of participation). The maximum number of positive screens by any individual was 8/9. Most (48%) participants had 3-4 positive screens, while 29% had 1-2 positive screens and 22% had more than 4 positive screens. More importantly, using the VA screen for PTSD, **41% screened positive for PTSD.** Most participants (95%) screened positive for combat trauma exposures, half met the VA screening criteria for MST, and 10% the VA screen for TBI. Thus, the mental health care needs of this group are substantial.

**In this study, RNG servicewomen reported our web-based MH screening and tailored educational intervention for post-deployment readjustment provided needed education they felt they otherwise would not have received (48%), decreased MH stigma (32%) and improved access as two-thirds indicated they would subsequently seek MH care (38% VHA and 26% non-VA care).** Participating women endorsed the online interface for improving subsequent access to mental health care. **Almost a third (32%) reported that the tailored information they received reduced their discomfort with seeking care, 38% indicated that they would subsequently seek assessment from a VA provider, and 26% would do so from a non-VA provider.** The online method of education was shown to be a preferred source of information by users. The majority of participants (74%) indicated they preferred to receive VA information through e-mail and 66% routinely use the internet to seek health information. Most (74%) participants would recommend this web-based educational interface to other military women.

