Sampling: Subjects will be selected through the Defense Manpower Data Center (DMDC) with which [name] has a successful working relationship. Our previous work, on which this study builds, used military e-mail as the sole method of contact. We learned several lessons: (1) RNG servicewomen only sporadically checked their military e-mails which was problematic for recruitment; (2) feedback from participants told us that e-mailing a traditional IRB study invitation and informed consent (6-7 pages) was a participation deterrent; (3) we were unable to follow up with non-responders and determine a true response rate because our original QUERI sampling specifications to DMDC did not request additional information. Consequently, we have revised our protocol for recruiting: (1) we have increased the recruitment and follow-up duration; (2) we have worked with our IRB and Pharos Innovations (developer of the web-based program) to streamline the subject information and consent process; and (3) we have thus revised our DMDC registry requirements to sample potential participants with both e-mail and postal mail. Our respondents will be contacted initially by postal mail with study materials and web-based study link and notification that an e-mail is being mailed the same week for their convenience. Non-responders will be re-contacted in 10 days following initial mailing. DMDC is able to provide sociodemographic and military information (e.g. age, marital status, race, rank, number of deployments) that will subsequently allow us to compare study participants with refusals and non-responders. This will facilitate follow up and better analysis of the generalizability of findings. Web-based interface participants will be reimbursed \$30.00 for their participation.

Sample Size: Taking into account a conservatively estimated e-mail only response rate (15%) and response rates based on letter contact and phone follow-up (48% - 70%), we conservatively estimate a 20% response rate using e-mail and letter recruitment and therefore will request a sample of 2,000 women from DMDC to achieve a final sample size of 400. Assuming conservatively that 30% of the sample will screen positively for PTSD (45% of RNG women participating in our original QUERI web-based screen met criteria for PTSD), this will allow us to have at least 120 women with a positive screen for PTSD.

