Descriptive statistics will be used to analyze individual items and mean scores on each of the various screens. Estimated power for within group mean differences (i.e., paired t-tests) based on the smaller of the two groups (i.e., N=400: 120 PTSD positive/280 PTSD negative) and assuming a conservative variance=2 and a mean difference of .5, then power=97%. A larger sample size n=280), a smaller observed variance, or a larger observed mean difference would all provide additional power. The power to detect mean differences between groups (120 PTSD positive v. 280 PTSD negative) assuming a conservative variance=2 and a mean difference is calculated to be of .5, then power=90%. Power estimates for differences in proportions are expectedly lower but are estimated to be over 90% to detect medium effect sizes (>.4) and 54% to detect small (>.2) effect sizes. Using nQuery 4.0 for power calculation, we found we can detect a 25% difference in the proportion of women with mental health service use (which can be measured for all participants using VA databases) comparing NCM with existing outreach with 81% power using a simple test of proportions. Using logistic regression for the dependent variable of mental health service use and adjusting for covariates such as comorbid substance abuse, depression, and other post-deployment problems, we estimate that we can detect an odds ratio of 2.3 with 84% power or 2.0 with 76% power for NCM vs existing outreach. Given the appealing and personal nature of the concierge NCM, we believe we will find a large OR of these magnitudes.

OMB Considerations: Our QUERI RRP that serves as the foundation for this CREATE proposal was exempt from OMB review since the survey and collection of information being conducted was in connection with research to prevent a clinical disorder (identified as a basis for exemption under 5 CFR 1320.3). We anticipate that this will be the case with this study as it addresses prevention of chronic PTSD entrenchment and associated mental health or social issues (e.g., depression, substance abuse, marital or family maladjustment). We readily obtained OMB exemption for our HSR&D and DoD funded studies with similar domains in OEF/OIF/OND servicewomen.

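### Screening prevalence is to be estimated from an expected 20% response with descriptive statistics only; the DMDC data planned for comparing responders with non-responders could also be used to weight the estimate

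*Combined protocol and SAP*

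**What the plan says.** Under Sample Size Analysis and Statistical Plan, the surveys built into the web interface "will be analyzed to estimate prevalence of post-deployment mental health concerns", among other descriptive outputs. The method named for the screens is: "Descriptive statistics will be used to analyze individual items and mean scores on each of the various screens". That section gives no weights, post-stratification, response model or non-response sensitivity analysis, and neither does any other.

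Under Sample Size, the plan states "we conservatively estimate a 20% response rate using e-mail and letter recruitment". It will therefore approach 2,000 women and expects 400 responders. Its working figure for positive screens is given as: "Assuming conservatively that 30% of the sample will screen positively for PTSD".

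Under Sampling, "DMDC is able to provide sociodemographic and military information"; the examples given are age, marital status, race, rank and number of deployments. The stated use is to compare participants with refusals and non-responders, which is meant to help follow-up and the assessment of generalizability. The same section says that the pilot could not determine a true response rate because its DMDC request lacked the needed information.

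Under Preliminary Work, the results of the pilot of this interface carry the caveat "recognizing the probable selection bias of participation".

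**The concern.** Prevalence is a stated estimation target. If four in five invited women do not answer, the responders' figure equals the population figure only if response is unrelated to the condition being screened. The plan acknowledges probable participation bias in its pilot, and its revised DMDC request is meant to supply information on the women who do not answer. The stated analytic use of that information is a comparison. A comparison can show that responders are, say, older or more often deployed, but the reported prevalence stays the same.

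At stake is how the prevalence figures are read. The sections on significance and on implications for policy and practice direct the results to several VA offices. A responders' figure could easily be taken there as the rate among Reserve and National Guard women returning from deployment.

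**Working it through.** **Inputs from the plan.** 2,000 women approached, 20% response and 30% screening positive (Sample Size); 3,000 eligible women in the four states (Study Feasibility).

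**The plan's own figures.** 2,000 × 0.20 = 400 responders and 400 × 0.30 = 120 positive. Both reproduce exactly.

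**Sampling error.** 1.96 × √(0.30 × 0.70 / 400) = 0.045, so a 95% interval would run from 25.5% to 34.5%. With a finite-population correction for 3,000 women, the half-width is 0.0449 × √(2,600 / 2,999) = 0.042. The plan specifies no interval for prevalence. This is simply what a usual one would show, and it would contain no allowance for selection.

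**Selection by response ratio (assumed).** If PTSD-positive women respond k times as often as PTSD-negative women, an observed 30% corresponds to a true rate of 0.30 / (0.70k + 0.30).

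| k (assumed) | True rate | Observed minus true |
|---|---|---|
| 0.67 | 39.0% | −9.0 points |
| 1.25 | 25.5% | +4.5 points |
| 1.5 | 22.2% | +7.8 points |
| 2 | 17.6% | +12.4 points |

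At k = 1.25 the bias already equals the sampling half-width.

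**Selection by non-responder prevalence (assumed).** True rate = 0.20 × 0.30 + 0.80 × (non-responder prevalence). Non-responder values of 20%, 25% and 40% give 22%, 26% and 38%. With no assumption at all, the bounds are 0.06 + 0 = 6% and 0.06 + 0.80 = 86%.

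**What weighting on a frame variable could recover (assumed).** Take two equal strata of 1,000 invited women, for example by number of deployments.

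- Larger contrast: response 28% and 12%, prevalence 36% and 16%. Unweighted: (280 × 0.36 + 120 × 0.16) / 400 = 30.0%. Weighted: (0.36 + 0.16) / 2 = 26.0%. The shift is 4.0 points. Kish effective n = 2,000² / (1,000²/280 + 1,000²/120) = 336, a design effect of 400 / 336 = 1.19.
- Milder contrast: response 25% and 15%, prevalence 35% and 21.7%. Unweighted 30.0%, weighted 28.3%, a shift of 1.7 points. Effective n = 2,000² / (1,000²/250 + 1,000²/150) = 375, a design effect of 1.07.

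Intervals widen by about √1.07 = 1.03 to √1.19 = 1.09, that is by 3% to 9%. The documents give no response rate or prevalence by DMDC variable, so no single corrected figure can be computed.

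**The case against.** The case on the other side is substantial, and much of it stands.

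- **Prevalence is secondary.** Aim 2 and Hypotheses 2.a and 2.b concern satisfaction, enrollment and service use by assigned route. No test or decision in the plan rests on prevalence. This stands and limits the priority.
- **The figure may be meant to describe participants.** The plan does not say that it will be projected to all Reserve and National Guard women. On that reading an unweighted figure is correct, but the report then has to say so, and the plan does not.
- **Non-response is already being addressed.** Compared with the pilot, the plan adds postal contact, re-contact at 10 days, longer recruitment and a shorter consent process, as well as the responder comparison. These steps may raise response. They do not adjust the estimate for the women who still do not answer.
- **Absence of weighting is inferred from silence.** True, but descriptive statistics are the only method named.
- **The gain may be small.** Both illustrated shifts are below the 4.5-point sampling half-width and rest on assumed strata. If the DMDC variables predict neither response nor a positive screen, weighting changes almost nothing.

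A reader might also infer that weighting would remove an error of 8 to 12 points. The documents do not support this. Those values assume that PTSD status itself drives response, in one direction only, and frame variables capture just part of such selection. Stigma and avoidance of care, which the plan itself lists as barriers, could push the bias the other way.

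Nor do the documents show that complete data are held on every non-responder. They say what DMDC can provide, with examples, and do not state how complete it is for each woman.

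**Conclusion.** The point holds as a cheap improvement of minor priority. The plan makes prevalence an estimation target, expects 20% response, and gives the non-responder data no role in the estimate. Possible selection bias is comparable to or larger than the 4.5-point sampling half-width and may go either way, with true rates from 17.6% to 39.0% against an observed 30% over the assumed response ratios. Weighting would address only the part explained by DMDC variables, 1.7 to 4.0 points in the illustrations and possibly less. All response ratios, non-responder rates and stratum values are assumptions; only the 2,000, 20%, 400, 30% and 3,000 come from the plan.

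A reader might infer that the randomised comparison of nurse case manager with outreach is biased as well. It is not: randomisation takes place among women who have already responded and screened positive, so survey non-response affects whom the result applies to, not its internal validity.

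**What to change.** In the statistical plan, for the screening prevalence estimates only:

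1. Prespecify inverse-probability-of-response weights from a logistic model for response among all invited women. Use the DMDC variables actually available (age, marital status, race, rank, number of deployments) and state, which defines the sampling frame. Say how missing frame data will be handled.
2. Report weighted prevalence with robust standard errors beside the unweighted figures.
3. Describe the unweighted figures as applying to respondents only, and note that weighting does not remove selection on symptoms within levels of the DMDC variables.

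Leave satisfaction and intention to seek care, both asked after the interface, as unweighted descriptions of participants. Non-responders never saw the interface, so weighting those answers to them would describe a hypothetical reaction, not an existing proportion.

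The cost is a little more analysis with data the plan already intends to request, and slightly wider intervals (design effect about 1.07 to 1.19 in the illustrations). No extra participants, contacts or measurements are needed.
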